Visit	1	2 Baseline	3	4	5	6	7	8	EoT ²	FUP 1	EoS	
Day	-28 to -1	1 ¹	8	15	29	43	57	71	85	56 days after last drug admin.	112 days after last drug admin.	
Weeks	-4	0	1	2	4	6	8	10	12	8 weeks after last drug admin.	16 weeks after last drug admin.	
Time window for visits (days)	n.a.	none	±1	±1	±3	±3	±3	±3	±3	±7	+7	
Abscess count	X	X	X	X	X	X	X	X	X			
Inflammatory nodule count.												
Non-inflammatory nodule count												
Draining Fistula count.												
Photography		X			X				X			
Hidradenitis Suppurativa Clinical Response (HiSCR)			X	X	X	X	X	X	X			
International Hidradenitis Suppurativa Severity Score System (IHS4)	X	X	X	X	X	X	X	X	X			
Hidradenitis Suppurativa Area Severity Index (HASI)		X	X	X	X	X	X	X	X			
Hidradenitis Suppurativa Physician's Global Assessment (HS-PGA)	X	X	X	X	X	X	X	X	X			
Dermatology Life Quality Index (DLQI)		X	X		X		X		X			
Hidradenitis Suppurativa Quality of Life (HiS-QoL)		X	X		X		X		X			
FACIT-Fatigue scale		X	X		X		X		X			
Patient Global Assessment of Change (PGI-C)			X		X		X		X			
Patient Global Assessment of Severity (PGI-S)		X	X		X		X		X			
Columbia-Suicide Severity rating Scale (C-SSRS) ¹²	X	X	X	X	X	X	X	X	X	X	X	

Trial Periods	Screening	Treatment Period								EoT	Safety Follow-Up	
Visit	1	2 Baseline	3	4	5	6	7	8	EoT ²	FUP 1	EoS	
Day	-28 to -1	1 ¹	8	15	29	43	57	71	85	56 days after last drug admin.	112 days after last drug admin.	
Weeks	-4	0	1	2	4	6	8	10	12	8 weeks after last drug admin.	16 weeks after last drug admin.	
Time window for visits (days)	n.a.	none	±1	±1	±3	±3	±3	±3	±3	±7	+7	
Dispense Patient's Diary ¹³	X	X	X	X	X	X	X	X				
Review returned Patient's Diary ¹⁴		X	X	X	X	X	X	X	X			
All adverse events ¹⁵	X	X	X	X	X	X	X	X	X	X	X	
Concomitant therapy	X	X	X	X	X	X	X	X	X	X	X	
Roll over into OLE trial ¹⁶									X			
Completion of patient participation											X	

1 Day of Randomization / Day of first intake of randomized medication. If needed, some visit 2 assessments may be conducted 2 days before or after the actual visit date after consultation with the Sponsor.

2 Patients who discontinue trial treatment prematurely-should undergo the End of Treatment (EoT) visit as soon as possible. All patients not entering the OLE trial are expected to complete the EoT visit, a FUP1 visit 8 weeks after their last trial drug intake and a final EoS visit 16 weeks after their last trial drug intake. For patients entering the OLE trial at week 12, the EoT visit will be their EoS visit in trial 1368-0052. (see also footnotes #8 and #16)

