Patients who permanently discontinue trial drug earlier than week 12, or do not qualify to enter the OLE trial for any other reason, will be invited to do the EoT visit instead of the next planned visit and will then enter a 16 weeks safety follow-up period. The first visit in the safety follow-up period will be scheduled 8 weeks after their last study drug administration and the second visit will be scheduled 16 weeks after their last study drug administration. This is the end of study visit and patients will finish their participation in the study after completing this visit.

[figure not shown]

Figure 3.1:1 Trial Design

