3.3.4 Withdrawal of patients from treatment or assessments

Patients may discontinue trial treatment or withdraw consent to trial participation as a whole ("withdrawal of consent") with very different implications; please see [sections 3.3.4.1](#) and [3.3.4.2](#) below.

Every effort should be made to keep the patients in the trial: if possible, on treatment, or at least to collect important trial data.

Measures to control the withdrawal rate include careful patient selection, appropriate explanation of the trial requirements and procedures prior to trial enrolment, as well as the explanation of the consequences of withdrawal.

The decision to discontinue trial treatment or withdraw consent to trial participation and the reason must be documented in the patient files and CRF. If applicable, consider the requirements for Adverse Event collection reporting (please see [sections 5.2.6.1](#) and [5.2.6.2](#)). If the reason for discontinuation is death, this should be reported on the SAE form as well, regardless of causal relationship.

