3.3.4.1 Discontinuation of trial treatment

An individual patient will discontinue trial treatment if:

- The patient wants to discontinue trial treatment, without the need to justify the decision.
- The patient has repeatedly shown to be non-compliant with important trial procedures and, in the opinion of both, the investigator and sponsor representative, is not willing or able to adhere to the trial requirements in the future.
- The patient needs to take concomitant medication such as
 - immunosuppressive agents (including biologics),
 - systemic corticosteroids for HS,
 - opioid analgesics
 - systemic antibiotics for HS before week 4
 - Systemic antibiotics for HS without meeting criteria for disease worsening (as defined in [Section 4.2.2.2](#))
 - metformin (unless on a stable dose for 12 weeks before visit 2 for a non-HS indication)
 - spironolactone (unless on a stable dose for 12 weeks before visit 2 for a non-HS indication)
 - live vaccines.
 - The patient can no longer receive trial treatment for medical reasons (such as major surgery, adverse events, other diseases, malignancies as per [Section 4.2.1.3](#), or pregnancy). If a hepatic injury alert (as defined in [Section 5.2.6.1.4](#)) is confirmed without identification of an alternative cause in the work-up according to the “DILI checklist” the patient should not receive subsequent doses of trial treatment
- The patient develops suicidal ideation or any suicidal behavior (See [Section 4.2.1.4](#))
- For individual stopping rules related to specific adverse events, please see [section 4.2.1](#) other treatments and emergency procedures.

In case of a temporary reason, trial treatment should be restarted if medically justified, please see [section 4.1.4](#).

For all patients the reason for withdrawal from trial treatment (e.g. adverse events) must be recorded in the CRF. This data will be included in the trial database and reported.

If new efficacy/safety information becomes available, Boehringer Ingelheim will review the benefit-risk-assessment and, if needed, pause or discontinue the trial treatment for all patients or take any other appropriate action to guarantee the safety of the trial patients.

Even if the trial treatment is discontinued, the patients remain in the trial and, given their agreement, should undergo the procedures for early treatment discontinuation and follow-up as outlined in the [Flowchart](#) and [section 6.2.3](#).

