4.2.2.3 Antibiotic use during the trial

Non HS use:

Systemic antibiotics can be used for indications other than HS and for a duration of less than or equal to 4 weeks during the entire course of the trial (from randomization up to the last treatment administration).

HS disease worsening (as defined above in [section 4.2.2.2](#)):

At or after week 4, if the patient requires systemic antibiotics for disease worsening as per the investigator, monotherapy with either doxycycline 100mg orally twice daily or alternative as per investigator discretion, may be used for a maximum period of 2 weeks, and not more than a total of 4 weeks during the entire course of the trial.

Concomitant use of systemic antibiotic therapy for treatment of HS other than for disease worsening, or before week 4, is not allowed and will lead patient to permanent treatment discontinuation (see [Section 3.3.4.1](#)).

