4.2.2.5 Lesion intervention

In the event that an acutely painful lesion occurs that requires immediate intervention, physicians will have the option to perform protocol-allowed interventions.

Only two types of interventions are allowed: Intra-lesional steroid and Incision and Drainage (I&D). If I&D is performed, only over the counter antiseptic wash can be used. Concomitant medications associated with the lesion intervention must be captured in the medical records. A total of two protocol-allowed interventions are permissible. An intervention can maximally occur on two different lesions at the same time or on the same lesion at two different study visits. If the subject requires more than two interventions, then they may be discontinued from the study.

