5.2.6.2 Adverse event collection and reporting

5.2.6.2.1 AE Collection

The investigator shall maintain and keep detailed records of all AEs in the patient files. For patients not rolling over to OLE trial, the following must be collected and documented on the appropriate CRF(s) by the investigator:

- From signing the informed consent onwards until the individual patient's end of study:
all AEs (serious and non-serious) and all AESIs.
- After the individual patient's end of study:
the investigator does not need to actively monitor the patient for new AEs but should only report any occurrence of cancer and trial treatment related SAEs and trial treatment related AESIs of which the investigator may become aware of by any means of communication, e.g. phone call. Those AEs should be reported on the BI SAE form (see [section 5.2.6.2.2](#)), but not on the CRF.

For patients rolling over to OLE trial the following must be collected and documented on the appropriate CRF(s) by the investigator:

- From signing the informed consent of the parent trial onwards until the first dose of trial medication in the extension trial:
all AEs (serious and non-serious) and all AESIs.

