6.2.3 Follow-up period and trial completion

For all randomized patients termination of trial medication (EoT) and trial completion (EoS) must be recorded on the corresponding CRFs.

For patients completing the randomized trial treatment regularly at Week 12 (EoT) and not rolling-over to the OLE trial, safety follow-up visits will be performed at Week 20 (FUP1 Visit) and at Week 28 (EoS, EoS Visit).

Patients who roll-over to the OLE trial will complete their participation in the trial at week 12 (EoT visit)

Early treatment discontinuation

Patients who discontinue treatment prematurely prior to the planned EoT visit (Week 12) should be registered as withdrawn from treatment in IRT.

Patients should follow the scheduled visits as much as possible as defined in the [Flowchart](#), this is: the EoT should be conducted either immediately or as soon as possible, followed by the FUP1 visit 8 weeks after the last trial drug administration date and the EoS visit 16 weeks after the last trial drug administration date. All efforts should be made to keep the patient in observation for at least 16 weeks after the last dose of the study drug.

Treatment completion

Treatment completion is defined as a patient having completed treatments till planned EoT visit (Week 12).

Trial completion:

Trial completion is defined as a patient having reached the EoS Visit per protocol (or rolled-over to OLE trial and therefore have completed an EoT/EoS visit).

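### The lesion-intervention rule lets a site take a patient out of the study, where the rest of the protocol stops treatment only and keeps the patient under follow-up

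*Protocol*

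**What the plan says.** Section 4.2.2.5 allows intralesional steroid or incision and drainage for an acutely painful lesion, up to two interventions in total. For a patient who needs more, the rule is: "If the subject requires more than two interventions, then they may be discontinued from the study". It does not refer to another section and gives no exit procedure.

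Elsewhere the protocol describes stopping as follows:

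- **Section 3.3.4** names two routes: "Patients may discontinue trial treatment or withdraw consent to trial participation as a whole". It stresses that they have different implications.
- **Section 3.3.4.1** lists the reasons for stopping treatment. A need for more than two lesion interventions is not among them. The section then says: "Even if the trial treatment is discontinued, the patients remain in the trial".
- **Section 3.1** says that patients who stop drug early, or do not enter the extension trial for another reason, "will be invited to do the EoT visit instead of the next planned visit and will then enter a 16 weeks safety follow-up period".
- **Flowchart footnote 2** says: "All patients not entering the OLE trial are expected to complete the EoT visit, a FUP1 visit 8 weeks after" the last drug intake, with EoS at 16 weeks.
- **Section 6.2.3** says of early stoppers: "All efforts should be made to keep the patient in observation for at least 16 weeks after the last dose of the study drug".
- **Section 4.2.2.3**, the antibiotic rule, deals with a similar situation. Antibiotics for HS before Week 4, or without disease worsening, "is not allowed and will lead patient to permanent treatment discontinuation", with a cross-reference to 3.3.4.1.

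**The concern.** A patient who needs a third lesion intervention meets two different instructions. The lesion rule points to leaving the study. All the general rules point to stopping drug and staying under observation. A site that follows 4.2.2.5 as written could close the patient out without an EoT lesion count and without FUP1 and EoS.

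The safety consequence is the firmer one. Under section 5.2.6.2.1, once a patient who does not roll over has reached the end of study, "the investigator does not need to actively monitor the patient for new AEs". After that point only cancers and treatment-related SAEs and AESIs that happen to come to the investigator's attention are reported, and they go on the SAE form, not the CRF. Yet section 7.2.5 counts AEs as treatment-emergent until 16 weeks after the last dose, and SAP section 6.1 runs the on-treatment period to last dose plus 112 days. SAP section 7.8.1 analyses the number of patients with AEs. A patient who left early would therefore stay in the denominator while new events were no longer actively sought.

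There is also an efficacy point. Repeated intervention for painful lesions reflects disease activity, so an EoT count lost on this ground is lost for a reason tied to the outcome. Finally, SAP section 7 tabulates withdrawal from the trial before EoT separately from premature discontinuation of trial medication. Under the present wording, different sites could put the same kind of patient in different rows.

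**Working it through.** **1. Does any text resolve the conflict?**

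| Place | What stops | What follows |
|---|---|---|
| 4.2.2.5 | study (optional) | nothing stated |
| 4.2.2.3 | treatment (mandatory) | refers to 3.3.4.1 |
| 3.3.4.1 | treatment | patient stays in the trial |
| 3.1, 6.2.3, footnote 2 | treatment | EoT, then FUP1 and EoS |
| 3.3.4.2 | participation | only by withdrawal of consent |

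Nothing says that 4.2.2.5 means treatment only. No section defines removal from the study by the investigator.

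**2. AE observation lost per patient, on the literal reading**

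- Residual effect period: 16 weeks × 7 = 112 days (7.2.5).
- Assumed time of leaving: 0 to 14 days after the last dose. Fourteen days is the longest planned gap between doses (Week 2 to Week 4, then every two weeks).
- Days left without active collection: 112 − 0 = 112, and 112 − 14 = 98.
- As a share: 112/112 = 100%, and 98/112 = 87.5%.
- Weight of one patient in the planned arms of 30 and 15: 1/30 = 3.3% and 1/15 = 6.7%.

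**3. Samples and assessments lost (flowchart and Table 10.1:1)**

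- PK: samples 1 to 10. Sample 9 is FUP1 and sample 10 is EoS, so 2 of 10 are lost.
- ADA/Nab: samples 1, 3, 4, 6, 8, 9 and 10, seven in all. Samples 9 and 10 are lost, so 2 of 7.
- If EoT (sample 8) is also missed: 3 of 10 and 3 of 7.
- Also lost: C-SSRS and pregnancy tests at FUP1 and EoS, and the safety laboratory and ECG at EoS.

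**4. Effect on the primary endpoint**

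The plan's own figure reproduces. Section 7.5 gives an 80.1% chance of observing a difference of at least 30 points when the true reductions are 62% and 20% and the SD is 45.

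- Standard error: 45 × √(1/30 + 1/15) = 14.23.
- Φ((42 − 30)/14.23) = 80.05%. A gamma simulation gives 80.08%.

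As an illustration of lost precision only, without bias:

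| Patients without a Week 12 value | n per arm | SE | Probability |
|---|---|---|---|
| none | 30 / 15 | 14.23 | 80.05% |
| one per arm | 29 / 14 | 14.64 | 79.4% |
| three per arm | 27 / 12 | 15.61 | 77.9% |

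These losses are not attributable to the wording alone. An early stopper has EoT as soon as possible and no lesion counts at FUP1 or EoS, so the Week 12 count is mostly missing whichever word is used. What the wording puts at risk is the early EoT count, which may fall in an earlier analysis window.

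**The case against.** The best defence is that the general rules already cover this patient. Someone taken off under 4.2.2.5 has stopped drug and is not entering the extension trial, so section 3.1, footnote 2 and section 6.2.3 apply on their face. Withdrawal of consent is the patient's own act, so a stop initiated by the investigator can only be a treatment discontinuation. The list in 3.3.4.1 is also open-ended about medical reasons. For patients not rolling over, end of study is defined as the visit 16 weeks after the last dose, and Table 6.7:1 of the SAP places it at last dose plus 112 days even for early stoppers unwilling to follow the full schedule. On that reading, AE collection covers the whole residual period. The lesion rule is optional, its frequency is unknown, and the trial is exploratory.

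Much of this stands. Loss of data is possible, not certain, and a careful site could reach the right answer by reading across sections. The efficacy effect looks small and its direction is open.

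The wording remains a problem all the same. The defence asks the site to read *study* as *treatment*, and no text tells it to. The antibiotic rule in the same part of the protocol names treatment and gives the reference, so the different word here can be taken as deliberate. A visit scheduled at 112 days does not help if the site believes that the patient has already left.

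**Conclusion.** The concern holds. Section 4.2.2.5 offers an exit that section 3.3.4 does not define and that conflicts with the rules keeping patients who stop treatment in the trial.

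The figure of 98 to 112 days is per patient. It rests on three assumptions: the site applies the sentence literally, it uses the option, and the patient leaves within 14 days of the last dose. No trial-level figure can be given, because the documents contain no rate of patients needing a third intervention. No size or direction of efficacy bias is claimed. This is a correction that should be made to protect the residual-period safety data and the EoT count. It does not put the validity of the trial in doubt.

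**What to change.** - In 4.2.2.5, replace the end of the sentence so that the patient *may be discontinued from trial treatment (see Section 3.3.4.1)*.
- In 3.3.4.1, add a need for more than two lesion interventions to the list of reasons for stopping treatment.
- State that such a patient remains in the trial for EoT with lesion counts, FUP1 and EoS.

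The cost is one changed sentence and one bullet. The three visits are already in the flowchart, so no visit or procedure is added.

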4.2.2.6 Restrictions on diet and life style

No specific restrictions on diet or life style of the patients are required.

4.2.2.7 Contraception requirements

WOCBP (for the definition please refer to [section 3.3.2](#)) must use highly effective methods of birth control per ICH M3 (R2) that result in a low failure rate of less than 1% per year when used consistently and correctly during the trial, and for a period of at least 16 weeks after the last study drug administration. A double barrier method of contraception is not

required. A list of contraception methods meeting these criteria is also provided in the patient information.

Female Patients

Acceptable methods of birth control for this trial are:

- Combined (estrogen and progestogen containing) hormonal birth control that prevents ovulation (oral, intravaginal, transdermal)
- Progestogen-only hormonal birth control that prevents ovulation (oral, injectable, implantable)
- Intrauterine device (IUD) or intrauterine hormone-releasing system (IUS)
- Bilateral tubal occlusion
- Vasectomised sexual partner with documented absence of sperm

Or

Patients must abstain from male-female sex. This is defined as being in line with the preferred and usual lifestyle of the patient. Periodic abstinence e.g. calendar, ovulation, symptothermal, post-ovulation methods; declaration of abstinence for the duration of exposure to study drug; and withdrawal are not acceptable.

Male Patients:

Contraception of male trial participants and female partners of male trial participants are not required.

4.3 TREATMENT COMPLIANCE

Administration of the study medication will be done in the study center under the supervision of the investigator or a designee. The measured plasma concentrations will provide additional confirmation of compliance.

5. ASSESSMENTS

5.1 ASSESSMENT OF EFFICACY

The primary, secondary and further endpoints of the study are specified in sections [2.1.2](#) and [2.1.3](#), and [2.2.2](#), respectively.

1. The **HiSCR (Hidradenitis Suppurativa Clinical Response)** is one of the most well-known and widely used outcome assessment in clinical trials. HiSCR is defined as at least a 50% reduction from baseline in the total abscess and inflammatory nodule count, with no increase in the abscess or draining fistula count. [\[R20-2976\]](#)
HiSCR will be evaluated at the timepoints mentioned in the [Flowchart](#) and the detail is provided in [Appendix 10.2](#)
2. **IHS4 – IHS4** is a valid, clinical scoring system for dynamic assessment of HS severity. Determining IHS4 requires counting nodules, abscesses and draining fistulae/sinus tracts making it straightforward to apply in clinical trials [\[R20-3045\]](#). IHS4 will be evaluated at the timepoints mentioned in the [Flowchart](#) and the detail is provided in [Appendix 10.3](#)
3. **HS-PGA** – This documents the physician’s assessment of the patient’s HS at a given timepoint. It scores patient disease severity as either clear or minimal or mild or moderate to severe or very severe, based on abscesses, draining fistulae, inflammatory nodule and non-inflammatory nodule [\[R20-3046\]](#). HS-PGA will be evaluated at the timepoints mentioned in the [Flowchart](#) and the detail is provided in [Appendix 10.4](#)
4. **HASI** - HASI is modelled after the Psoriasis Activity and Severity Index (PASI). Four classic signs of HS-related inflammation (erythema, induration, open ulcer and draining tunnels) are included. Each variable in HASI is scored on a Likert scale (0–3) for each predetermined body region. For BSA assessment, the number of palms (one palm indicated 1% of the patient’s BSA) involved for each body region (head, right axilla, left axilla, anterior chest, back, anterior bathing trunk, posterior bathing trunk, other) is assessed. This is converted to a percentage of that region. An area score was assigned to each region using the PASI approach (0 = none, 1 = 1–9%, 2 = 10–29%, 3 = 30–49%, 4 = 50–69%, 5 = 70–89%, 6 = 90– 100%). To calculate the regional HASI score, the sum of the four clinical variable scores is multiplied by the area score of each involved region. This value is then multiplied by the proportion of the BSA of that region, to give a regional HASI score. Regional HASI scores are added together to give the cumulative total HASI score (range 0–72). HASI will be evaluated at the timepoints mentioned in the [Flowchart](#) and the detail is provided in [Appendix 10.5](#)
5. **Pain NRS**
The HS Pain NRS is an endpoint for the assessment of HS-related pain severity for clinical trials with patients with HS. As it is a unidimensional measure of pain intensity and can be administered daily with minimal subject burden. Recall period is 24h and response is given by an 11-point scale ranging from 0 to 10. [Appendix 10.6](#)
6. **DLQI**
The Dermatology Life Quality Index (DLQI) is a patient-administered, ten-question, quality of life questionnaire that covers six domains including symptoms and feelings, daily activities, leisure, work and school, personal relationships and treatment [\[R05-2548\]](#). The DLQI has a one-week recall period. Response categories include “not

relevant” (score of 0), “not at all” (score of 0), “a little” (score of 1), “a lot” (score of 2) and “very much” (score of 3). Question 7 is a “yes”/ “no” question where “yes” is scored as 3.

The DLQI will be analyzed under six headings as follows [[R05-2548](#)]:

Domain	Question Number	Score
Symptoms and feelings	Questions 1 and 2	Score maximum 6
Daily activities	Questions 3 and 4	Score maximum 6
Leisure	Questions 5 and 6	Score maximum 6
Work and school	Question 7	Score maximum 3
Personal Relationships	Questions 8 and 9	Score maximum 6
Treatment	Question 10	Score maximum 3

DLQI total score is calculated by summing the scores of each question resulting in a range of 0 to 30 where 0-1 = no effect on patient’s life, 2-5 = small effect, 6-10 = moderate effect, 11-20 = very large effect, and 21-30 = extremely large effect on patient’s life. The higher the score, the more the quality of life is impaired. If one question is left unanswered this is scored 0 and the total score is summed and expressed as usual out of a maximum of 30; for analysis by subscore only, the corresponding subscore is considered to be missing. If 2 or more questions are left unanswered (missing), DLQI total score is treated as missing. A 4-point change from baseline is considered a clinically important difference. [Appendix 10.7](#)

7. HiS-QoL (hidradenitis suppurativa quality of life)

HiS-QoL is a patient-administered, 17-item instrument to measure HS-specific quality of life in clinical trials with a 7-day recall period [[R20-3156](#)]. The 17-item HiS-QoL included four symptom items, eight activity-adaptation items and five psychosocial items. The item scores are summed to create a total ranging from 0 to 68, with higher scores indicating more severe impact on HRQOL. The subscale scores range from 0 to 16 for symptoms, 0 to 20 for psychosocial and 0 to 32 for activities-adaptations. [Appendix 10.8](#)

8. FACIT-Fatigue

The FACIT-Fatigue is a 13-item questionnaire ([[R10-6433](#)], [[R07-4311](#)], [[R16-0029](#)]) that assesses self-reported fatigue and its impact upon daily activities and function. Answers are based on a 5-point Likert scale. Responses of “not at all,” “a little,” “somewhat,” “quite a bit,” and “very much” are available for each question, and correspond to scores of 0, 1, 2, 3, and 4, respectively (total score range: 0-52). A minimal clinically important difference (MCID) of 3-4 points in change score has been reported [[R16-0029](#)]. The recall period for items is 7 days. [Appendix 10.9](#)

